5.1.1.3 Effectiveness Analyses

Effectiveness analyses in the CP will be based on the mITT Population. Effectiveness analyses in the TP (12-Month) and Repeat Treatment Period will be performed on the VIT and VRT populations, respectively. Effectiveness assessments are defined as follows:

Table 5-5 Effectiveness Assessments

Assessment/Term	Description
AIHS	Assessed by the EI 0 - None 1 - Mild 2 - Moderate 3 - Severe 4 - Extreme
GAIS	Assessed by participant and EI based on 5-point GAIS 2 - Much improved 1 - Improved 0 - No change -1 -Worse -2 - Much worse
FACE-Q appraisal of lower eyelids	Participant responses to the following question on a scale 1-Not at all 2-A little 3-Moderately 4-Extremely Questions include if they are bothered by Excess fat under eyes Excess skin under eyes Puffiness under eyes How noticeable are the lines under eyes Crepey (wrinkled) skin under eyes How old the area under the eyes makes them look How tired the area under the eyes makes them look
[REDACTED]	[REDACTED]
[REDACTED]	[REDACTED]
[REDACTED]	[REDACTED]

Baseline assessments for applicable effectiveness endpoints defined as follows:

Table 5-6 Effectiveness Endpoint Baseline Definitions

Endpoint	Description

 • AIHS (EI) 	Baseline refers to the evaluation at screening

 • FACE-Q Appraisal of Lower Eyelids module 	Baseline refers to the evaluation at randomization or initial treatment

5.1.1.3.1 Primary Effectiveness Endpoint

The primary effectiveness endpoint is the responder rate at Month 3 after the last treatment. A responder is defined as a participant who shows at least 1-point improvement from baseline on the AIHS in both infraorbital areas based on EI assessment. Baseline is defined as the EI assessment at screening.

For the primary effectiveness analysis, a 2-sided, Fisher’s exact test at the 5% level will be used to test whether the responder rate at Month 3 in the treatment group is significantly greater than that in the control group at Month 3 in the control period. The 95% CI by Wald test will be provided.

[figure not shown]
The primary effectiveness analysis will be performed on the mITT population using multiple imputation, as specified in [Section 5.1.1.1.5](#). Sensitivity analysis will be performed using as-observed and LOCF data, as described in [Section 5.1.1.1.5](#).

Descriptive analysis on the responder rates in the TP (12-Month) for the VIT population will also be provided. The responder rate from the treatment group at Month 3 will also be summarized by the primary injection instrument used (needle or cannula) and by median volume injected.

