### **3.2 Clinical Hypotheses**

The responder rate at Month 3 in the treatment period will be significantly greater than that in the control group at Month 3 in the control period, and the majority of subjects will have clinically significant improvement in infraorbital hollowing at Month 3.

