#### **4.5 Treatment Allocation Ratio**

Subjects are randomized at an allocation ratio of 3:1 to treatment with VOLBELLA XC or no treatment control group.

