### **5. Study Population**

#### **5.1 Number of Subjects**

Up to 175 subjects will be enrolled at up to 15 sites in order to randomize 140 subjects and have an estimated 112 subjects complete the study based on an anticipated 20% screen fail rate and dropout rate of 20% during the study.

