5.1.1.1.4 Statistical Methodology

When indicated, 95% 2-sided CIs and 2-sided p-values will be presented. Individual endpoint analyses may specify exceptions (additions or deletions) to these general definitions.

Descriptive statistics will be presented for key outcome measures. Categorical variables will be summarized with frequency and relative frequency. Continuous variables will be summarized by number of participants, mean, median, standard deviation, 1st and 3rd quartiles, minimum, and maximum. Where appropriate, 2-sided 95% CIs for population mean, or population proportion, will be provided as part of the descriptive summary. 2-sided p-values will be presented when indicated.

Raw and derived data listings will be provided, and will be fully defined in the table, figure, and data listing specification document.

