5.1.1.1.5 Missing Data

Missing data handling conventions for the primary endpoint is specified and summarized as follows:

Table 5-3 Missing Data Handling by Endpoint Type

Parameter type	Timing	Missing Data Handling
Responder	Month 3 (treatment period for treatment group and control period for the control group)	
 • All participants included (mITT population) • Multiple imputation with 5 imputed datasets is applied to participants with no Month 3 values using the below model: $\text{Month 3 AIHS} = \beta_0 + \beta_1 \text{Baseline AIHS} + \beta_2 \text{Month 1 AIHS}$. This is performed by treatment group and by side (left and right).
Responder	Month 3 (treatment period for treatment group and control period for the control group)	
 • All participants included (mITT population) • LOCF for participants with no Month 3 values

Note: Missing baseline will be replaced with the average of all non-missing baseline values of all participants.

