5.1.2 Determination of Sample Size

Table 5-10 **Sample Size Assumptions**

Parameter	Assumption/Estimate
Primary endpoint	
Risk difference	
A	
Sides	
Power	
N per group	
N total	

5.2 **Changes in the Conduct of the Study or Planned Analyses**

The primary analysis was changed from as-observed to multiple imputation so that all participants in the mITT will be used for statistical inference.

5.2.1 **Changes in the Conduct of the Study**

Not applicable.

5.2.2 **Changes to Analyses Prior to Database Lock**

Not applicable.

6. Data Handling and Analysis Conventions

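### The Wald 95% CI for the primary effect has a lower limit that is too favourable at plausible (assumed) responder rates; the Fisher test is not affected.

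*SAP*

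**What the plan says.** SAP 5.1.1.3.1 tests the Month 3 responder rate, treatment against control, with a two-sided Fisher's exact test at 5%. A responder improves by at least 1 AIHS point in both infraorbital areas. The next sentence is "The 95% CI by Wald test will be provided". That section does not say whether the interval is for the difference or for each arm's rate, and it mentions no continuity correction.

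Other relevant places:

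- SAP 5.1.1.1.4 sets the level: "When indicated, 95% 2-sided CIs and 2-sided p-values will be presented". The nominal error is therefore 2.5% per tail.
- SAP Table 5-10 has a row headed "Risk difference", with its value redacted. This supports reading the interval as one for the difference.
- SAP Table 5-3 gives the missing-data method: "Multiple imputation with 5 imputed datasets is applied to participants with no Month 3 values using the below model". SAP 5.2 explains that multiple imputation replaced the as-observed analysis "so that all participants in the mITT will be used for statistical inference". Neither place gives a rule for combining the interval over the imputed datasets.
- Protocol 4.5: "Subjects are randomized at an allocation ratio of 3:1". Protocol 5.1 plans enrolment "in order to randomize 140 subjects and have an estimated 112 subjects complete the study".
- Protocol 3.2 expects that "the majority of subjects will have clinically significant improvement in infraorbital hollowing at Month 3".

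**The concern.** The plan uses an exact test for the comparison but a large-sample interval for the effect size. The Wald standard error takes p(1-p)/n from each arm at the observed rate. When an observed rate is close to 0 or 1 this term is too small, and with no responders in an arm it is zero. Here both arms may lie towards the ends of the scale: a high rate after treatment, and a low rate in a small untreated arm that must improve on both sides. With a high treated rate and a low control rate, the shortfall works mainly against the lower limit, so the smallest benefit compatible with the data is overstated.

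This is the only interval that 5.1.1.3.1 attaches to the primary comparison in a pivotal study. It is the figure a reader would use to judge how large the benefit is at least.

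**Working it through.** **Group sizes.** The plan's own chain reproduces exactly: 112/(1 - 0.20) = 140 and 140/(1 - 0.20) = 175. At 3:1, 140 × 3/4 = 105 treated and 140 × 1/4 = 35 control.

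**Rates.** The planned responder rates are redacted. The assumed grid is treated 70, 80 or 90% with control 2, 5, 10, 15 or 20% (15 cells), and treated 50 or 60% with control 2, 5, 10, 15, 20 or 30% (12 cells). Treated rates of 50% and above follow the hypothesis in Protocol 3.2; low control rates are a judgement about an untreated arm.

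**Intervals for the difference, z = 1.96.**

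- Wald: pT - pC ± z √[pT(1-pT)/nT + pC(1-pC)/nC], with observed rates.
- Continuity-corrected Wald: widen each side by 0.5(1/nT + 1/nC).
- Agresti-Caffo: the Wald formula with pT = (xT+1)/(nT+2), pC = (xC+1)/(nC+2), and denominators nT+2 and nC+2.

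**Method.** Enumerate all outcomes of the two binomials at 105:35. Sum the probability that the lower limit exceeds the true difference (lower-tail error) and that the upper limit falls below it (upper-tail error).

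**Uncorrected Wald, complete data.**

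| Treated | Control | Lower-tail error | Coverage |
|---|---|---|---|
| 70-90% | 2-20% | 4.5-8.2% | 91.2-94.4% |
| 50-60% | 2-30% | 3.3-5.2% | 93.3-94.9% |

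The lower-tail error is above 2.5% in all 27 cells. Single pairs:

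| Treated vs control | Wald lower / upper | Corrected Wald lower | Agresti-Caffo lower |
|---|---|---|---|
| 60% vs 30% | 3.91% / 2.05% | 2.48% | 2.44% |
| 70% vs 20% | 4.81% / 1.65% | 2.98% | 2.21% |
| 80% vs 15% | 5.32% / 1.43% | 3.12% | 1.74% |
| 80% vs 10% | 5.54% / 1.21% | 3.88% | 1.32% |

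**Higher control rates (outside the grid).** The Wald lower-tail error is 4.1% at 80% vs 30%, 3.4% at 80% vs 40% and 2.8% at 80% vs 60%. At 90% vs 70% it is 2.1%, with 4.2% in the upper tail.

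**Cause.** At 90% vs 5% the lower-tail error is 7.7% at 105:35 and still 5.4% at 105:350. The small control arm is only part of the problem; the high treated rate contributes too.

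**Continuity correction.** Over the grid the lower-tail error is at most 4.8% (treated 70-90%; above 2.5% in 13 of 15 cells) and at most 3.0% (treated 50-60%; 6 of 12 cells).

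**Agresti-Caffo.** On the grid at 105:35 the lower-tail error is at most 2.4%. The upper-tail error is above 2.5% in 25 of 27 cells and reaches 3.9%.

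**Effect on a reported limit: 84/105 vs 4/35.**

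- Wald: 0.8000 - 0.1143 = 0.6857; SE = √(0.8000×0.2000/105 + 0.1143×0.8857/35) = 0.0665; lower limit 0.6857 - 1.96×0.0665 = 55.5%.
- Agresti-Caffo: 85/107 - 5/37 = 0.7944 - 0.1351 = 0.6593; SE = √(0.7944×0.2056/107 + 0.1351×0.8649/37) = 0.0685; lower limit 52.5%.

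Other tables: 63/105 vs 10/35, 13.8% to 12.7%; 84/105 vs 7/35, 44.7% to 42.5%; 84/105 vs 0/35, 72.3% to 67.5%; 95/105 vs 0/35, 84.9% to 79.2%.

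**Imputation.** A stand-in simulation at 105:35 imputed responder status within arm, with 5-20% missing at random, 5 imputations and Rubin's rules. The pooled Wald lower-tail error was 3.7-8.2% (treated 70-90%) and 2.8-4.7% (treated 50-60%). It does not use the SAP's by-side AIHS model, so it shows only that pooling does not by itself remove the excess.

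**The case against.** The strongest reply is that nothing is decided by this interval. Success rests on Fisher's test, and no margin or threshold is tied to the lower limit. The FACE-Q analysis depends on the primary endpoint being met, not on the CI. That stands, and it limits the importance of the point. A reader might infer that the primary test is anti-conservative or that a success claim is at risk; the documents do not support this, because the test is exact and separate from the interval.

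A second reply is that the size depends on redacted rates and on where the grid stops. This also stands. A reader might infer that the Wald limit is always too favourable here, but the documents give no control rate, and the excess fades or reverses when that rate is high. Total coverage is also milder than the single tail suggests: on average 93.0% for treated 70-90% and 94.0% for treated 50-60%.

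A third reply is that Agresti-Caffo is not evenly balanced either. That is correct: it moves most of the imbalance to the upper tail. The case for it is that its error runs towards understating the benefit.

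Two further limits apply. The missing label is mainly a wording gap, since the sentence follows a between-group test. And completer numbers (112, or 84:28) should not be taken as the primary analysis set: the SAP imputes missing Month 3 values for the mITT population, and the 20% dropout is for the whole study.

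**Conclusion.** The concern holds as one about the reported precision of the primary effect. At 105:35, over the assumed grid, the uncorrected Wald lower limit is too favourable in 3.3-8.2% of trials instead of 2.5%. A continuity correction, if one was intended, would reduce this without always removing it.

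The conclusion rests on three assumptions: the interval is for the risk difference, it is uncorrected, and the control rate is low to moderate. The direction is firm within the grid. The size is uncertain because the planned rates are redacted and because the exact figures are for complete data. It is a change worth considering, at low cost, and not a threat to the trial's main conclusion.

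**What to change.** In SAP 5.1.1.3.1:

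1. State that the 95% CI is for the difference in Month 3 responder rates, treatment minus control.
2. Replace Wald with Agresti-Caffo (add one responder and one non-responder to each arm, then compute the difference and its standard error).
3. For the primary analysis, do this in each of the 5 imputed datasets and pool by Rubin's rules. Keep the unadjusted difference as the point estimate.
4. Use the same interval for the as-observed and LOCF analyses, so that the three differ only in how missing data are handled. A different interval for the sensitivity analyses would defeat this.

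The cost is two or three sentences and a few lines of code. In the tables tried, the reported lower limit falls by about 1 to 6 points. The interval will not be centred on the observed difference, and it leans conservative for benefit, with the upper-tail excess shown above.

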5.1.1.4 Secondary Effectiveness Endpoint

The secondary effectiveness analyses will include the responder rates with 95% CIs for the treatment group based separately on the EI and participant assessments of GAIS, where a “responder” is a participant who shows improvement in the overall aesthetic assessment in the infraorbital area (Improved or Much Improved on GAIS) at the Month 3 Visit, and participant responses on the validated Appraisal of Lower Eyelids module of the FACE-Q questionnaire. A 2-sided paired t-test at the 5% level will be performed to demonstrate that the mean overall satisfaction score at Month 3 visit is statistically greater than that at baseline for the treatment group.

The secondary effectiveness analysis for Satisfaction with validated Appraisal of Lower Eyelids module of the FACE-Q questionnaire will be conducted only if the primary endpoint is met. No additional multiplicity adjustment or gatekeeping multiple comparisons procedures are needed.

5.1.1.5.1 Study Treatment Exposure

Study treatment exposure will be measured by volume injected at each treatment. Summary of volume injected will be provided by side of the face at initial, touch-up, and repeat treatments as well as the combination of the initial and touch-up treatments.

5.1.1.6 Administration of Study Treatment

Variables related to administration of treatment listed below will be summarized for safety population by treatment group and by side of the face if appropriate at initial, touch-up and repeat treatment as follows:

- Pretreatment anesthesia type (ice, topical, and local)
- Planes of injection [REDACTED]
- Injection technique [REDACTED]
- Injection instrument (needle, cannula, or both)
- Primary injection instrument used (needle or cannula)
- Injection ease (0 [Difficult] to 10 [Easy] scale)
- Product moldability (0 [Stiff] to 10 [Moldable] scale)

5.1.1.6.1 Adverse Events

An AE will be considered a TEAE if:

- The AE began on or after the date of the first dose of study intervention; or
- The AE was present before the date of the first dose of study intervention, but increased in severity or became serious on or after the date of the first dose of study intervention; or
- For the control group, AE began on or after the date of randomization; or
- For the control group and prior to the initial treatment, if AE was present before randomization, but increases in severity on or after randomization date, the AE is considered as TEAE.

An AE will be considered a treatment-emergent SAE if it is a TEAE that additionally meets any SAE criteria.

AEs and encompassing abnormalities, reported as occurring after the Screening Visit, will be coded using MedDRA version 20.1 or newer. A listing for all TEAEs in the treatment and control groups will be presented. AEs that occur before initial treatment for the treatment group and randomization for the control group will be listed. Additionally, unique participants reporting AEs as well as the number of events in the following AE categories will be summarized for treatment participants, control participants after optional treatment, and all treated participants as follows:

Table 5-7 AE Summaries

Endpoint	Description	Timing	Methodology
Overall summary	Overall summary only for the following categories: 
 • TEAEs • Treatment-related TEAEs • Treatment-related TEAEs at injection site • Treatment-related TEAEs not at injection site • SAEs • Treatment-related SAEs • Treatment-related SAEs at injection site • Treatment-related SAEs not at injection site • Discontinued due to TEAE • Deaths 	
 • CP • TP (12-Month) • Repeat Treatment Period • TP (9-Month) 	Categorical counts, Event descriptive
TEAEs	
 • Overall Summary and by SOC, PT 		Categorical counts, Event descriptive
TEAEs	
 • Overall summary and by SOC, PT and severity 		Categorical counts, Event descriptive
Treatment-related TEAEs	
 • Overall summary and by SOC, PT 		Categorical counts, Event descriptive
	
 • Overall summary and by SOC, PT and severity 		
	
 • Summary by duration, time to onset, severity, causality, treatment required, and outcome 		

Note: SOCs and PTs will be sorted in descending frequency in the treatment group, then control group. AEs for control group before and after optional treatment are summarized separately.

For participants who receive repeat treatment, their AEs reported during the first months in the initial treatment period will be summarized and presented in parallel with AEs reported during the repeat treatment period.

Overall summary by severity for TEAEs and treatment-related TEAEs will also be summarized by the primary injection instrument used (needle vs cannula).

If more than 1 AE is coded to the same PT for the same participant, the participant will be counted only once for that PT using the most severe and most related occurrence for the summarizations by severity and by relationship to study intervention.

Time to onset for TEAEs will be computed as

$$\text{AE start date} - \text{reference date} + 1,$$

where the reference date is initial treatment date for TEAEs occurring on or after initial treatment but before touch-up treatment and the reference date is touch-up treatment date for TEAEs occurring on or after touch-up treatment but before repeat treatment.

Duration for TEAEs will be computed as AE end date – AE start date + 1. If AE end date is not available, duration for TEAEs will not be computed.

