### **11.1.3 Serious Adverse Event**

An SAE is defined in accordance with ISO 14155 as an AE that:

- a) led to death,
- b) led to serious deterioration in the health of the subject, that either resulted in
  1. a life-threatening illness or injury, or
  2. a permanent impairment of a body structure or a body function, or
  3. in-patient or prolonged hospitalization, or

4. medical or surgical intervention to prevent life-threatening illness or injury or permanent impairment to a body structure or a body function
- c) led to fetal distress, fetal death or a congenital abnormality or birth defect

NOTE: Planned hospitalization for a pre-existing condition, or a procedure required by the protocol, without serious deterioration in health, is not considered an SAE. Allergan considers all cancer AEs as SAEs. Abortion is also considered an SAE except for elective abortion of a normal fetus.

See [Section 11.4](#) for procedures for reporting an SAE/serious adverse device effect (SADE).

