### **11.1.8 Severity**

Severity is a clinical determination of the intensity of an adverse event. The severity assessment for a clinical adverse event is to be completed using the following definitions as guidelines:

Mild	Awareness of sign or symptom, but easily tolerated
Moderate	Discomfort affecting daily activity
Severe	Disabling with inability to do usual daily activities

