5.1.1.1.2 Analysis Populations

The analysis populations will consist of participants as defined below:

Table 5-2 Analysis Populations

Population	Definition	Study Treatment
mITT	
 • Participants who were randomized to study treatment (treatment group), received at least 1 study device treatment, and had baseline and at least 1 post-treatment assessment of the primary effectiveness variable • Participants who were randomized to the control group and have baseline and at least 1 follow-up assessment of the primary effectiveness variable 	Randomized assignment
Safety	
 • Participants who were randomized to study treatment (treatment group) and received at least 1 study device treatment • Participants who were randomized to the control group 	Actual received ^a
VIT Population	
 • Participants who were randomized and received VOLBELLA treatment at the beginning of the Control Period 	Actual received
VRT Population	
 • Participants in the VIT population who received VOLBELLA repeat treatment 	Actual received
VOT Population	
 • Participants who were randomized to control group and received VOLBELLA optional treatment after the Control Period 	Actual received

^a If a randomized control participant does not receive the optional treatment, the actual received treatment will be assigned as control treatment.

Effectiveness analyses in the CP will be performed on the mITT population using the “as-randomized” assignment for each participant (i.e., if a participant randomized to the control group is treated inadvertently at the start of the study, the assessments for that participant will nonetheless be included in the control group analysis). Effectiveness analyses in the TP (12-Month) and Repeat Treatment Period will be performed on the VIT and VRT populations, respectively.

Safety analyses in the CP will be conducted on the safety population using the actual received treatment. Safety analyses in the TP (12-Month), Repeat Treatment Period, and TP (9-Month) will be performed on the VIT, VRT, and VOT populations, respectively.

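### The treatment-emergent rule for an adverse event already present at baseline omits the became-serious limb for untreated controls, so one rare type of event is classified differently by arm (minor)

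*SAP*

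**What the plan says.** SAP 5.1.1.6.1 lists four alternative ways for an AE to become treatment-emergent. The first two are anchored to the first dose: onset on or after it, or presence before it with the event having "increased in severity or became serious on or after the date of the first dose of study intervention". The last two are for controls and are anchored to randomization. One covers new onset: "For the control group, AE began on or after the date of randomization; or". The other, limited to controls before their initial treatment, covers events already present: "if AE was present before randomization, but increases in severity on or after randomization date, the AE is considered as TEAE".

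The same section adds: "An AE will be considered a treatment-emergent SAE if it is a TEAE that additionally meets any SAE criteria".

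The protocol separates the two concepts. Section 11.1.8 states: "Severity is a clinical determination of the intensity of an adverse event". Section 11.1.3 defines seriousness by outcome, one of the listed outcomes being "in-patient or prolonged hospitalization, or".

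On where the definition is used, SAP 5.1.1.1.2 puts all participants randomized to control in the safety population and states: "Safety analyses in the CP will be conducted on the safety population using the actual received treatment". Table 5-7 lists the Control Period among the timings for its summaries. The note below it says that control events before and after optional treatment are summarized separately.

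**The concern.** The control bullets exist so that an untreated arm, which has no first dose, still has a treatment-emergent count to set beside the treated arm. That works only if the two sets of rules are parallel. The onset rules are. The rules for events already present are not, because the treated version has two limbs (worse grade, or became serious) and the control version has one.

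Severity and seriousness are separate in the protocol, and the SAP's own first-dose bullet lists them as alternatives. A rise in grade therefore cannot be read as covering the missing limb. Since a treatment-emergent SAE must first be a TEAE, the omission carries through to that definition too. At stake is whether the Control Period AE tables of a pivotal study apply one definition to both arms. The category left out for controls is a serious one.

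**Working it through.** The plan gives no figure to reproduce here, and the sample-size table is blacked out. The check is a comparison of rules on one test case, followed by an illustration of scale.

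**Test case.** An AE starts after consent and before randomization, keeps the same severity grade, and meets an SAE criterion during the Control Period.

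| Bullet in SAP 5.1.1.6.1 | Treated participant | Control before treatment |
|---|---|---|
| 1. Onset on or after first dose | Not met (earlier onset) | Cannot apply (no dose given) |
| 2. Present before first dose, then worse grade or became serious | **Met** (became serious) | Cannot apply (no dose given) |
| 3. Control: onset on or after randomization | Not applicable | Not met (earlier onset) |
| 4. Control: present before randomization, then worse grade | Not applicable | Not met (grade unchanged) |
| TEAE? | Yes | No |
| Treatment-emergent SAE? | Yes | No |

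Later optional treatment does not bring the control event back under bullet 2, because it became serious before that first dose. No other section of the SAP or protocol supplies the missing limb.

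**Can such events occur?** AE collection starts at consent (Protocol 11.1.1). Randomization may be on the same day or up to 30 days later (Protocol 6.2.2). The window is therefore 0 to 30 days. Initial treatment should be on the day of randomization (Protocol 6.2.3.1), so the two anchors are otherwise comparable.

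**Scale.** Inputs are 140 randomized (SAP 4.1.2) and 3:1 allocation (Protocol 4.5).
- Treated: 140 × 3/4 = 105. Control: 140 × 1/4 = 35.
- One affected participant: 1/35 = 2.9 percentage points in controls, and 1/105 = 1.0 point in treated.

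The documents give no rate for such events. Let p be an assumed chance per participant. The expected number of controls left out is 35p, and the chance of leaving out at least one is 1 − (1 − p)^35. The expected number counted among the treated is 105p.

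| Assumed p | Expected controls left out | Chance of at least one | Expected treated counted |
|---|---|---|---|
| 0.1% | 0.035 | 3.4% | 0.105 |
| 0.5% | 0.175 | 16.1% | 0.525 |
| 1% | 0.35 | 29.7% | 1.05 |
| 2% | 0.70 | 50.7% | 2.10 |

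Up to an assumed 1%, zero affected controls is the most likely result.

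**The case against.** The difference in wording cannot be disputed. The case on the other side is about consequence, and most of it stands.

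- **No between-group estimate is planned.** Table 5-7 specifies categorical counts and descriptive event summaries, with no difference, interval or test. Control Period safety also uses treatment actually received. A reader might infer a biased treated-minus-control estimate of harm, but the SAP specifies no such estimate.
- **The SAE rows may be unaffected.** They are labelled *SAEs*, not treatment-emergent SAEs. A reader might infer that the SAE comparison is distorted. That follows only if the rows use the treatment-emergent definition, which the SAP does not say. If they count all SAEs in the period, only the TEAE rows are affected, and a control could then appear as an SAE without being a TEAE.
- **The affected set is very narrow.** Signs and symptoms that predate treatment are not AEs unless they recur or worsen (Protocol 11.1.1), so stable medical history does not enter. Apart from death and fetal outcomes, the SAE criteria require a serious deterioration in health, and the note to Protocol 11.1.3 excludes planned hospitalization without one. Grades are defined by effect on daily activity (Protocol 11.1.8), so an event that leads to unplanned admission would usually rise in grade unless already severe, and would then meet the fourth bullet.
- **The event is not lost.** SAP 5.1.1.6.1 lists control AEs that occur before randomization. Protocol 11.2 requires SAEs to be reported within 24 hours of awareness, from consent onward. The event is missing from a count, not from the safety record.
- **The direction is unfavourable to the device.** The gap cannot hide device harm.

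One further argument does not stand. The sentence introducing Table 5-7 names treated participants and controls after optional treatment, which might suggest that untreated controls are not summarized. The Control Period timing in the table, the note below it and SAP 5.1.1.1.2 show that they are.

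**Conclusion.** Wrong as written, minor. The control rule is strictly narrower than the treated rule for events already present at baseline, and nothing else in the documents closes the gap. It can only under-count controls in the Control Period TEAE summaries, and in the SAE rows if those mean treatment-emergent SAEs.

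The likely effect is nil or close to it. One affected control would move the control percentage by 2.9 points. This assumes that 140 are randomized exactly 3:1 and that all 35 controls stay in the control column. A reader might take a range such as 0 to 2 controls (2/35 = 5.7 points) as an estimate, but the documents give no rate to support it. No hypothesis test, error rate, power or success criterion is involved. Confidence is high for the difference in definition and does not extend to any claim of material impact.

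**What to change.** In the fourth TEAE bullet of SAP 5.1.1.6.1, insert *or becomes serious* directly after *increases in severity* and leave the rest of the bullet as it is. The opening limits (control group only, before initial treatment) must stay. The bullets are joined as alternatives, so without those limits the rule would apply to everyone and would anchor treated participants to randomization instead of first dose.

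In the same edit, state whether the SAE rows of Table 5-7 count all SAEs in the period or treatment-emergent SAEs only.

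The cost is three words in the bullet, one clarifying phrase and one condition in the TEAE flag. No other analysis changes and no additional data are needed.
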